7.2.3. Pharmacokinetic and Pharmacodynamic Analyses

This section describes the PK/PD analyses in addition to those specified in Section 7.2.1. The assessment of population-PK may be considered using data from this study or in combination with data from other studies. Assessments of ALXN1210 PK/PD relationships may be explored using data from this study or in combination with data from other studies. Total C5 serum concentrations will be evaluated in the same way as free C5 serum concentrations.

7.3. Safety Analyses

All safety analysis will be conducted on the Safety Set. All safety data available at the time of database lock up to Day 183 will be provided in patient listings.

7.3.1. Study Duration, Treatment Compliance, and Exposure

Summary statistics (mean, SD, median, minimum, and maximum) will be produced for the following using the Safety Set:

- Number of infusions from Day 1 to Day 183
- Number of patients receiving 1, 2, etc maintenance doses prior to Day 183
- Total number of patients with an infusion interruption as well as total number of infusions interrupted from Day 1 to Day 183
- Duration of study participation calculated as the time in days from the signing of informed consent until the date of completion/discontinuation from the Primary Evaluation Period/Day 183 (ie, study duration = date of completion/discontinuation - date of informed consent + 1).
- Total time on study treatment (days) calculated as the time in days from first study drug infusion date until the last study drug infusion date from the Primary Evaluation Period (ie treatment duration = last study drug infusion date from the Primary Evaluation Period - first study drug infusion date + 1). Note that dosing on Day 183 represents the start of the Extension Period and will not be included in these calculations.

The frequency and percentage of patients who had a percentage of drug compliance range by increments of 10% (ie $\geq 100\%$; $\geq 90\%$ to $< 100\%$; $\geq 80\%$ to $< 90\%$; etc) will also be included.

This will be calculated as follows:

Percent compliance = total number of study drug infusions taken from Day 1 to end of Primary Evaluation Period (excluding Day 183 study drug infusion) / total number of expected infusions to end of Primary Evaluation Period (excluding Day 183 study drug infusion).

By-patient listings will be produced for study duration, treatment compliance and exposure.

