9.2. Treatments Administered

Patients will receive a loading dose of ALXN1210 on Day 1, followed by maintenance dosing of ALXN1210 on Day 15 and q8w thereafter for patients weighing \geq 20 kg, or q4w for patients weighing \leq 20 kg, as shown in Table 6. With the agreement of the Alexion Medical Monitor, the 600 mg loading dose may be given to patients weighing \geq 5 to \leq 10 kg as 2 separate infusions administered no more than 24 hours apart. Dosages are based on the patient's body weight recorded on the day of dosing or the most recently recorded weight. For patients entering the study on eculizumab therapy, Day 1 of study treatment will occur 2 weeks from the patient's last dose of eculizumab.

Table 6:	Loading and Maintenance Treatment Regimen	IS

Body Weight Range (kg) ^a	Loading Dose (mg)	Maintenance Doses (mg)	Maintenance Dosing Frequency
\geq 5 to < 10	600 ^b	300	q4w
$\geq 10 \text{ to} < 20$	600	600	q4w
\geq 20 to < 30	900	2100	q8w
\geq 30 to < 40	1200	2700	q8w
\geq 40 to < 60	2400	3000	q8w
\geq 60 to < 100	2700	3300	q8w
≥ 100	3000	3600	q8w

Abbreviations: q4w = once every 4 weeks; q8w = once every 8 weeks

With the agreement of the Alexion Medical Monitor, administration of a supplemental dose of ALXN1210 is permitted.

After the Primary Evaluation Period, all patients will roll over into an Extension Period and continue their weight-based maintenance dose of ALXN1210 on Day 183 and q8w thereafter for patients weighing ≥ 20 kg, or q4w for patients weighing ≤ 20 kg, until the product is registered or approved (in accordance with country specific regulation) or for up to 4 years, whichever occurs first, except in Norway where the Extension Period will be 4 years.

The actual time of all dose administrations, including any supplemental dose or dose administered as 2 separate infusions as noted above, will be recorded on the patient's eCRF.

^a Dose regimen will be based on body weight obtained at the study visit. If the study drug needs to be prepared the night prior to the visit, the weight from the previous visit may be used.

b With the agreement of the Alexion Medical Monitor, the 600 mg loading may be given to patients weighing ≥ 5 to < 10 kg as 2 separate infusions administered no more than 24 hours apart.

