4. DESCRIPTION OF THE PROTOCOL

ALXN1210-PNH-304 is a Phase 3, open-label, single-arm multicenter study to evaluate the PK/PD, safety, and efficacy of ALXN1210 administered by intravenous (IV) infusion to pediatric patients (< 18 years of age) with paroxysmal nocturnal hemoglobinuria (PNH). The study consists of a 4-week Screening Period, a 26-week Primary Evaluation Period, and an Extension Period.

Patients will receive a loading dose of ALXN1210 on Day 1, followed by maintenance dosing of ALXN1210 on Day 15 and q8w thereafter for patients weighing ≥ 20 kg, or q4w for patients weighing < 20 kg, as shown in Table 2. With the agreement of the Alexion Medical Monitor, the 600 mg loading dose may be given to patients weighing ≥ 5 to < 10 kg as 2 separate infusions administered no more than 24 hours apart. Dosages are based on the patient's body weight recorded on the day of dosing or the most recently recorded weight. For patients entering the study on eculizumab therapy, Day 1 of study treatment will occur 2 weeks from the patient's last dose of eculizumab.

Table 2: Loading and Maintenance Treatment Regimens

Body Weight Range (kg) ^a	Loading Dose (mg)	Maintenance Doses (mg)	Maintenance Dosing Frequency
≥ 5 to < 10	600 ^b	300	q4w
≥ 10 to < 20	600	600	q4w
≥ 20 to < 30	900	2100	q8w
≥ 30 to < 40	1200	2700	q8w
≥ 40 to < 60	2400	3000	q8w
≥ 60 to < 100	2700	3300	q8w
≥ 100	3000	3600	q8w

^a Dose regimen will be based on body weight obtained at the study visit. If the study drug needs to be prepared the night prior to the visit, the weight from the previous visit may be used.

^b With the agreement of the Alexion Medical Monitor, the 600 mg loading may be given to patients weighing ≥ 5 to < 10 kg as 2 separate infusions administered no more than 24 hours apart.

Abbreviations: q4w = once every 4 weeks; q8w = once every 8 weeks

With the agreement of the Alexion Medical Monitor, administration of a supplemental dose of ALXN1210 is permitted.

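### The SAP 7.3.1 compliance ratio lets a supplemental infusion cancel out a missed scheduled dose

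*SAP*

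**What the plan says.** SAP 7.3.1 defines percent compliance as a ratio. The numerator is the "total number of study drug infusions taken from Day 1 to end of Primary Evaluation Period". The denominator is the "total number of expected infusions to end of Primary Evaluation Period". Both carry one exclusion, "excluding Day 183 study drug infusion". The word *expected* is not defined further. Results are tabulated as a "percentage of drug compliance range by increments of 10"%, with an open-ended top band of ≥ 100%.

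SAP section 4 gives the schedule as a loading dose on Day 1, then "maintenance dosing of ALXN1210 on Day 15 and q8w thereafter for patients weighing ≥ 20 kg, or q4w for patients weighing < 20 kg". The same section allows two kinds of infusion beyond one per scheduled day:

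- With the Medical Monitor's agreement, "administration of a supplemental dose of ALXN1210 is permitted". No limit on the number is stated.
- With the same agreement, the 600 mg loading dose for patients weighing ≥ 5 to < 10 kg may be given "as 2 separate infusions administered no more than 24 hours apart".

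Protocol 9.2 repeats both provisions. It also requires that the actual time of every administration, "including any supplemental dose or dose administered as 2 separate infusions as noted above, will be recorded on the patient's eCRF".

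**The concern.** A compliance ratio should show whether patients received the doses the plan called for. Here the numerator counts every infusion, scheduled or not, and no rule sets supplemental infusions aside. A supplemental dose given at any point before Day 183 can therefore stand in for a scheduled dose that was missed, and the patient reads as fully compliant. Patients with both events are those whose exposure departs most from plan, and for them the table would give a misleading figure. The top band is open-ended, so it also pools patients above 100% with those at exactly 100%.

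About 13 patients are planned (Protocol 14.2), and this SAP covers the report made after 12 are enrolled (SAP section 4). One patient in the wrong band moves a percentage in the total column by 1/13 = 7.7 to 1/12 = 8.3 points. The shift is larger within the naïve or previously eculizumab-treated group.

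**Working it through.** The documents state no compliance figure, so there is none to reproduce. The check applies the SAP ratio to the dosing schedule.

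**Inputs**
- Every 8 weeks (≥ 20 kg), before Day 183: Days 1, 15, 71, 127, so 4 scheduled infusions (SAP section 4; Protocol Table 1).
- Every 4 weeks (< 20 kg), before Day 183: Days 1, 15, 43, 71, 99, 127, 155, so 7 scheduled infusions (same sources).

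**Formulas**, with n scheduled, m missed and e extra infusions:
- SAP as written, with the expected count taken from the schedule: (n − m + e) / n
- Scheduled doses only: (n − m) / n

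**Supplemental infusion**

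| Regimen | Missed | Supplemental | SAP ratio | Scheduled only |
|---|---|---|---|---|
| 8-weekly | 1 | 0 | 3/4 = 75% | 3/4 = 75% |
| 8-weekly | 1 | 1 | 4/4 = 100% | 3/4 = 75% |
| 8-weekly | 0 | 1 | 5/4 = 125% | 4/4 = 100% |
| 4-weekly | 1 | 0 | 6/7 = 86% | 6/7 = 86% |
| 4-weekly | 1 | 1 | 7/7 = 100% | 6/7 = 86% |
| 4-weekly | 0 | 1 | 8/7 = 114% | 7/7 = 100% |

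One supplemental infusion moves a patient with one missed dose from the 70 to < 80% band (8-weekly) or the 80 to < 90% band (4-weekly) into ≥ 100%.

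**Split loading dose** (≥ 5 to < 10 kg only, so 4-weekly). The result depends on the undefined expected count:
- Day 1 counted once (7 expected): nothing missed gives 8/7 = 114%; one missed gives 7/7 = 100%.
- Day 1 counted as two (8 expected): nothing missed gives 8/8 = 100%; one missed gives 7/8 = 87.5%. The offset disappears.

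**Weight crossing 20 kg.** The denominator also needs a rule for these patients. Under the Table 1 footnote, a patient first reaching 20 kg at Day 43 is dosed on Days 1, 15, 43, 71 and 127, which is 5 infusions. One first reaching it at Day 99 is dosed on Days 1, 15, 43, 71, 99 and 127, which is 6. Neither 4 nor 7 is the right count for them.

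**The case against.** The strongest reply is that little depends on this number. Compliance enters no endpoint (SAP 5.1) and no analysis-set definition (SAP section 6). The study is descriptive, and PK calculations use actual dosing and sampling times (SAP 7.2.1). A reader might infer that the ratio distorts PK, PD or efficacy results; the documents do not support that.

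Masking also needs two events in the same patient, and the documents give no rate for either. Dosing is supervised (Protocol 9.9). SAP 7.3.1 also tabulates patients by number of maintenance doses before Day 183 and provides by-patient compliance and exposure listings. SAP 7.1.2 summarises and lists protocol deviations. With so few patients, these can be read case by case.

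All of that stands and limits the importance of the point. It does not correct the table. The maintenance count does not say whether a supplemental dose is included. As specified it is also not split by regimen: 3 maintenance doses before Day 183 is complete for an 8-weekly patient but half of the 6 due for a 4-weekly patient. The listings show the detail, but the summary still reports 100%.

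Two further inferences go too far. One is that any value above 100% is itself an error: the ≥ 100% band already accommodates such values, and the real problem is the offset. The other is that a split loading dose always inflates compliance: the SAP leaves *expected* undefined, and counting Day 1 as two is a tenable reading that removes the effect.

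**Conclusion.** The point holds, chiefly for supplemental doses. As worded, the rule returns 100% for a patient who missed one scheduled dose and received one supplemental infusion, where the scheduled doses give 75% (8-weekly) or 86% (4-weekly). This assumes only that the expected count follows the dosing schedule, and no passage provides for adding supplemental doses to it. The split-loading effect is conditional on Day 1 counting as one expected infusion and is confined to one weight band. How many patients would be affected cannot be told from the documents. The consequence is a misleading entry in a descriptive compliance table, not a threat to any endpoint or analysis set. It should be corrected, at modest priority.

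**What to change.** Amend the definition in SAP 7.3.1 as follows:

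- Numerator: scheduled dosing occasions before Day 183 at which study drug was infused. A split loading dose is one occasion.
- Denominator: scheduled occasions before Day 183 under the regimen that applied at each visit, so that patients crossing 20 kg get their own expected count.
- Supplemental infusions: tabulated separately, as number of patients and number of infusions, and left out of the ratio.
- State whether supplemental doses enter the infusion and maintenance-dose counts in the same section.

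Full receipt of the schedule then reads 100%, one missed dose reads 75% or 86% whatever else was given, and no value exceeds 100%. Because the numerator asks only whether drug was infused on an occasion, no new rule is needed for interrupted or partial infusions. The eCRF already records supplemental and split infusions, so no new data are required. The cost is a few lines of SAP text and minor programming, mainly for the visit-level expected count. This is a counting rule and changes no dosing.

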7.3.2. Adverse Events (AEs)

Adverse Events (AEs) will be classified by System Organ Class (SOC) and Preferred Term (PT) using the latest available version of MedDRA and will be reported by naïve, previously eculizumab-treated patients and total. The adverse events will be determined as occurring prior to treatment (pre-treatment) or as on or after first treatment (treatment-emergent) as described in Section 9.3. Analyses of Pre-Treatment Adverse Events (PTAEs) and Treatment-Emergent Adverse Events (TEAEs) will be tabulated and presented separately. Patients having multiple AEs within a category (e.g., overall, SOC, PT) will be counted once in that category. For severity/relationship tables, the patient's highest grade/most related event within a category will be counted. Percentages will be based on the number of treated patients in the Safety Set within naïve, previously eculizumab-treated patients and total. Tables will be sorted by descending frequency of SOC and by descending frequency of PT within SOC.

Listings will be provided for all TEAEs and PTAEs for the Safety Set.

Adverse events will include the displays described in the following sub-sections.

7.3.2.1. Overall Summary of Adverse Events

An overall summary table of TEAEs will be presented using summary statistics (n, %). The number of events (n) and number of patients with events (n, %) will be displayed for the following events subcategories:

- Total number of TEAEs and patients with TEAEs
- Related TEAEs
- Not related TEAEs
- Grade 1 TEAEs
- Grade 2 TEAEs
- Grade 3 TEAEs
- Grade 4 TEAEs
- Grade 5 TEAEs

Related AEs are defined as AEs that are possibly, probably, or definitely related to study treatment. Not related AEs are defined as AEs that are unlikely or not related to study treatment.

The number and percentage of patients who withdraw from the study due to an AE, who have any TEAE leading to study treatment discontinuation, or who died on study will be presented. These statistics will be prepared separately for SAEs, with the exception of severity grading.

7.3.2.2. AEs and SAEs by System Organ Class (SOC) and Preferred Term (PT)

The number of AEs and the number and percentage of patients with events will be presented by SOC and PT. SAEs will be summarized similarly.

7.3.2.3. AEs and SAEs by SOC, PT, and Relationship

The number of AEs and the number and percentage of patients with events will be presented by SOC and PT as described above by relationship (related, not related). In addition, AEs will be summarized as not related and related. If a patient has more than one occurrence of an AE, the strongest relationship to study treatment will be used in the summary table. Serious adverse events will be summarized similarly.

7.3.2.4. AEs by SOC, PT, and Severity

The number of TEAEs and the number and percentage of patients with events will be presented by SOC and PT as described above by severity (Grade 1, Grade 2, Grade 3, Grade 4, and Grade 5). If a patient has more than one occurrence of an AE, the highest grade will be used in the summary table.

7.3.2.5. Deaths, Other SAEs, and Other Significant Adverse Events

A listing of patient deaths will be produced, if applicable.

An important identified risk in this study is meningococcal infections. The adverse event of special interest (AESI) will be summarized by naïve, previously eculizumab-treated patients, and total.

7.3.3. Other Safety

7.3.3.1. Analyses for Laboratory Tests

Descriptive statistics by visit will be presented for each central laboratory parameter and for changes from baseline (continuous variables), by naïve, previously eculizumab-treated patients, and total. baseline is defined as the last non-missing assessment value prior to the first ALXN1210 infusion. Shift tables over time will be presented for all central laboratory values, where applicable, using normal, low, or high based on normal range values. For purposes of analyses, laboratory results based upon standardized units will be used. Individual patient plots as well as box plots will be presented for the following central lab parameters: hemoglobin, haptoglobin, hematocrit, reticulocytes, LDH, bilirubin, direct bilirubin, creatinine, AST, ALT, and GGT.

All central and local laboratory data will be presented in by-patient listings.

7.3.3.2. Physical Examination, Vital Signs, and Growth

Adverse changes from baseline in physical examination findings will be classified as AEs and analyzed accordingly.

Absolute values and changes from baseline in vital signs (blood pressure, heart rate, respiratory rate, and temperature) will be summarized descriptively at each visit, by naïve, previously eculizumab-treated patients, and total. Baseline is defined as the last non-missing assessment value prior to the first ALXN1210 infusion. The same method will be used to summarize height, weight, and head circumference (the latter only for patients ≤ 3 years of age).

By-patient data listings will be provided.

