To support regulatory filings, interim analyses may be conducted based on efficacy, safety, PK, PD, and immunogenicity data collected through the end of the 26-week Primary Evaluation Period (Day 183) after 12 patients are enrolled, and after enrollment is completed.

After completion of all pre-dose assessments on Day 183, all patients will enter an Extension Period and continue to receive ALXN1210 according to the appropriate weight-based regimen. The Extension Period will continue until the product is registered or approved (in accordance with country-specific regulations) or for up to 4 years, whichever occurs first, except in Norway where the Extension Period will be 4 years. The end of study is defined as the last patient's last visit or follow-up (whether on site or via phone call) in the Extension Period

Number of Patients (planned): Approximately 13 patients, from birth to < 18 years, will be enrolled to ensure at least 10 evaluable patients complete the 26-week period.

Diagnosis and Main Criteria for Inclusion and Exclusion:

Patients must meet all inclusion and no exclusion criteria. Patients who fail any of the eligibility criteria may be rescreened once for participation.

Inclusion Criteria:

- 1. Male and female patients < 18 years of age and weighing ≥ 5 kg at the time of consent.
- 2. Documented diagnosis of PNH, confirmed by high-sensitivity flow cytometry evaluation of red blood cells (RBCs) and white blood cells (WBCs), with granulocyte or monocyte clone size of \geq 5%.
- 3. For patients not currently treated with complement inhibitor, presence of 1 or more of the following PNH-related signs or symptoms within 3 months of Screening: fatigue, hemoglobinuria, abdominal pain, shortness of breath (dyspnea), anemia, history of a major adverse vascular event (including thrombosis), dysphagia, or erectile dysfunction; or history of packed RBC transfusion due to PNH.

- 4. Lactate dehydrogenase (LDH) values at Screening as follows:
 - a. For patients not currently treated with eculizumab, LDH level $\geq 1.5 \times \text{upper limit of normal}$ (ULN).
 - b. For patients who are currently taking eculizumab, LDH ≤ 1.5× ULN (sample must be obtained on a scheduled eculizumab-dosing day prior to dose administration [ie, at trough eculizumab level] and analyzed by the central laboratory).

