6.2.3. Safety Endpoints

The safety and tolerability of ALXN1210 will be evaluated from baseline to Week 26 and throughout the extension period by physical examinations, vital signs, physical growth (height,

weight, and head circumference [the latter only in patients who are ≤ 3 years of age]), electrocardiograms (ECGs), laboratory assessments, and incidence of AEs and serious adverse events (SAEs). The proportion of patients who develop antidrug antibodies (ADAs) will also be assessed.

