8.1. Inclusion Criteria

Patients are eligible for enrollment in the study only if they meet all of the following criteria and none of the exclusion criteria:

- 1. Male and female patients < 18 years of age and weighing ≥ 5 kg at the time of consent.
- 2. Documented diagnosis of PNH, confirmed by high-sensitivity flow cytometry evaluation (Borowitz, 2010) of red blood cells (RBCs) and white blood cells (WBCs), with granulocyte or monocyte clone size of \geq 5%.
- 3. For patients not currently treated with eculizumab, presence of 1 or more of the following PNH-related signs or symptoms within 3 months of Screening: fatigue, hemoglobinuria, abdominal pain, shortness of breath (dyspnea), anemia, history of a major adverse vascular event (including thrombosis), dysphagia, or erectile dysfunction; or history of packed red blood cell (pRBC) transfusion due to PNH.
- 4. Lactate dehydrogenase (LDH) values at Screening as follows:
 - a. For patients not currently treated with eculizumab, LDH level $\geq 1.5 \times \text{ULN}$.
 - b. For patients who are currently taking eculizumab, LDH $\leq 1.5 \times$ ULN (sample must be obtained on a scheduled eculizumab-dosing day prior to dose administration [ie, at trough eculizumab level] and analyzed by the central laboratory).
- 5. To reduce the risk of meningococcal infection (*N meningitidis*), all patients must be vaccinated against meningococcal infections within 3 years prior to, or at the time of, initiating study drug. Patients who initiate study drug treatment less than 2 weeks after receiving a meningococcal vaccine must receive treatment with appropriate prophylactic antibiotics until 2 weeks after vaccination. Patients who cannot be vaccinated must receive antibiotic prophylaxis for the entire treatment period and for 8 months following last dose.
- 6. Patients must have been vaccinated against *Haemophilus influenzae* type b (Hib) and *Streptococcus pneumoniae* according to national and local vaccination schedule guidelines, as appropriate.
- 7. Female patients of childbearing potential (ie, have achieved menarche) and male patients with female partners of childbearing potential must follow protocol-specified guidance for avoiding pregnancy while on treatment and for 8 months after last dose of study drug.

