14.9.2. Physical Examination, Vital Signs, and Growth

Adverse changes from baseline in physical examination findings will be classified as AEs and analyzed accordingly.

Vital signs will be summarized descriptively at baseline and postbaseline time points and for changes from baseline by treatment group.

Height, weight, and head circumference (the latter only for patients ≤ 3 years of age) will be summarized descriptively at baseline and postbaseline time points and for changes from baseline by treatment group.

By-patient data listings will be provided.

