5.3. Safety

The safety and tolerability of ALXN1210 will be evaluated from baseline to Week 26 and throughout the Extension Period by AEs and serious adverse events (SAEs), physical examinations, vital signs, physical growth (height, weight, and head circumference [the latter only in patients who are ≤ 3 years of age]), electrocardiograms (ECGs), and laboratory assessments. The proportion of patients who develop antidrug antibodies (ADAs) will also be assessed.

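### Growth is summarised only as raw measurements and raw changes from baseline, so the tables mainly reflect age and sex mix and cannot show whether growth is as expected

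*SAP*

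**What the plan says.** Protocol 6.2.3 and SAP 5.3 both list physical growth (height, weight and, up to age 3, head circumference) among the measures by which safety is judged.

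The population is wide. The Protocol synopsis plans "Approximately 13 patients, from birth to < 18 years, will be enrolled to ensure at least 10 evaluable patients complete the 26-week period". Inclusion criterion 1 in Protocol 8.1 reads "Male and female patients < 18 years of age and weighing ≥ 5 kg at the time of consent", and the highest dosing band starts at 100 kg.

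For the analysis, SAP 7.3.3.2 first describes vital signs: "Absolute values and changes from baseline in vital signs" are summarised descriptively at each visit, for treatment-naïve patients, previously eculizumab-treated patients and the total. It then says of growth: "The same method will be used to summarize height, weight, and head circumference". Protocol 14.9.2 plans the same kind of table; its growth measures "will be summarized descriptively at baseline and postbaseline time points and for changes from baseline by treatment group".

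SAP 7.2.1.2 plans no subgroups beyond prior eculizumab status. Age and weight categories appear in SAP 7.1.3.1 only as baseline descriptors. By-patient listings are planned for growth (SAP 7.3.3.2) and for demographics (SAP 7.1.3).

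**The concern.** The vital-signs method suits a measurement with no expected trend over 26 weeks. Height, weight and head circumference in children do have one, and its size depends on age and sex. A raw mean change in centimetres or kilograms therefore carries little information until the reader knows what the same children would have been expected to gain, and the planned tables supply no such value.

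Other safety data in the same SAP do get a yardstick. Laboratory values have shift tables against normal ranges (SAP 7.3.3.1), and QT and QTcF have fixed thresholds (SAP 7.3.3.3). Growth has none, although it is where the expected value depends most plainly on age.

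At stake is the readability of one named paediatric safety measure. The PK/PD primary endpoint is not affected.

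**Working it through.** **No figure to reproduce.** The study is descriptive, and the documents give no expected gain, SD or threshold for growth. The check is therefore a reading of the text followed by illustrations on assumed values.

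**Text.** Neither document mentions an SD score, z-score, percentile, growth velocity or age- and sex-specific reference for height, weight or head circumference. The planned statistics are n, mean, median, SD, minimum and maximum (SAP 7) of the raw value and the raw change. Within the primary period, height is measured at baseline and Day 183 only (Protocol Table 1 footnotes), so there is one change in height per child. Entry weight may run from 5 kg into the band starting at 100 kg, a span of at least 100/5 = 20-fold.

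**Effect of age mix on the mean.** Assume normal 26-week height gains of 5 cm for a toddler and 1 cm for a late adolescent. With k toddlers among n patients, all growing normally:

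mean change = (k × 5 + (n − k) × 1) / n

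- n = 13, k = 2: (2 × 5 + 11 × 1)/13 = 21/13 = 1.62 cm
- n = 13, k = 8: (8 × 5 + 5 × 1)/13 = 45/13 = 3.46 cm

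The mean roughly doubles with no child growing abnormally. If every child keeps its place relative to the reference, the mean change in SD score is about 0 in both cases.

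**Effect on the cohort columns.** The documents do not give the split by prior treatment. Taking columns of 5 for illustration:

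- 1 toddler: (1 × 5 + 4 × 1)/5 = 1.8 cm
- 4 toddlers: (4 × 5 + 1 × 1)/5 = 4.2 cm

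The columns differ by 2.4 cm through age mix alone.

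**One affected child.** A 3 cm shortfall in one patient moves the mean by 3/5 = 0.60, 3/10 = 0.30 or 3/13 = 0.23 cm at n = 5, 10 or 13.

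**All children affected.** A simulation (100,000 samples per setting) assumed normal 26-week gains spread uniformly over 0–4, 0.5–5 or 0–8 cm, a residual SD of 0.5 cm, and impaired growth at half the expected gain. It counted how often the impaired group's raw mean stayed above the lower 2.5% limit of normal group means:

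| n | Share not distinguished, across the three ranges |
|---|---|
| 5 | 33–61% |
| 10 | 2–17% |
| 13 | 0.3–7% |

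This favours the raw table, because the simulation knows the normal distribution of group means and the planned tables do not show it. For a single child at the top of each range, half-rate growth gives 2, 2.5 or 4 cm, which lies inside the normal all-ages range every time.

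**The case against.** A reader might infer that impaired growth could not be detected in this study, or that a child who stopped growing would be hidden by the others. The documents do not support that:

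- By-patient listings of growth and of demographics are planned. With about 13 patients, each child's baseline and Day 183 height can be set beside age and sex.
- Minimum and maximum are among the standard statistics, so a zero gain would appear as the minimum change. The table would not say whether it came from a late adolescent or a toddler, but the listings would.
- Both documents place growth under the physical examination (Protocol 11.2, SAP 5.3.4), and adverse changes in examination findings are to be classified as AEs (Protocol 14.9.2, SAP 7.3.3.2). On that reading, a growth problem recognised by the investigator would reach the AE tables.

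Other limits are also fair. Head circumference is confined to patients aged 3 or younger, so the wide age range applies to height and weight. The gains and toddler counts above are assumed, and the documents give no age distribution. The trial will have one age mix, which will be reported. This SAP covers only the 26-week report, and growth is not among the risks listed in Protocol 5.1.2.

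All of this stands, and it confines the point to the summary tables. It does not make those tables interpretable: a reader of the listings would still have to choose a reference and derive the scores after seeing the data. Small numbers do not excuse the omission either. Standardising needs no power, and age mix weighs more heavily on the mean when n is small.

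**Conclusion.** The point holds for the summary tables. Both documents reduce height and weight across the whole paediatric range, and head circumference up to age 3, to raw values and raw changes. Those tables, total and by cohort, mainly reflect age and sex mix and cannot show whether growth is as expected. In the illustration, mix alone moves the mean of 13 patients between 1.6 and 3.5 cm. The size rests entirely on the assumed gains of 5 and 1 cm and the assumed toddler counts; the direction needs only that expected growth varies with age and sex.

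The individual data are kept, so this is an avoidable gap in prespecification and not a loss of safety information. A reader might also infer that standardised scores would isolate a drug effect. They would not: without a control group, a change in SD score describes growth relative to the reference and cannot by itself be attributed to treatment. The change is worth making because it is cheap and the measure is a named safety endpoint.

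**What to change.** In SAP 7.3.3.2, add age- and sex-standardised SD scores for height, weight and, in patients aged 3 or younger, head circumference. Use one growth reference, named before database lock, and each child's age on the date of measurement. Summarise the SD score at baseline and Day 183, and its change, for treatment-naïve patients, previously eculizumab-treated patients and the total. Show the SD scores in the by-patient listings and keep the raw values.

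The cost is one derivation program. Sex, date of birth and the measurements are already in the plan, and no visit, sample or procedure changes. The real decision is the choice of a single reference for a sample drawn from about 10 sites globally, which is best made before the data are examined. The same derivation can serve the final CSR, since Protocol Tables 2 and 3 schedule heights at Days 575, 911, 1247 and 1639.
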